2.1.2 Statistics for Categorical Variables

For categorical variables such as gender, MACE, and TVF, results within treatment arm will be summarized with subject counts and percentages/rates, and where specified in the table mockups, with exact 95% Clopper-Pearson³ confidence intervals. Differences between the two treatment arms, when specified, will be summarized with the difference in percents and the Newcombe⁴ score 95% confidence interval for the difference of two percentages.

For efficacy and safety endpoint(s), relative risks (i.e., the ratio of rates), confidence interval for the relative risks, the difference in rates and the confidence interval for difference in rates (using previously-described formulas), and p-values may also be presented for hypothesis generating purposes. The p-values will be based on either Pearson's Chi-square test or Fisher's exact test by checking the expected frequency for each cell in the 2x2 contingency table against Cochran's rule⁶, i.e., if the expected frequencies for all cells are ≥ 5 , then Pearson's Chi-square test will be used, otherwise Fisher's exact test will be used.

For the determination of event rates at all time points (in-hospital, 30 days, 180 days and 1 to 7 (8/9/10) years), the denominators are defined as below based on the type of events.

- Death/MI/Revascularization (DMR) event

Subjects will be included in the analysis if they either had the DMR event by that time or they did not have the DMR event but had follow-up through that time point. In other words, subjects will be included in a given analysis if it can be determined whether or not the subject would have had the DMR event by the time point.

- Stent/Scaffold Thrombosis, Vascular/Bleeding, CVA, and Angina

Subjects will be included in the analysis if they either had the specific event (for example, for analysis on ST, only ST is considered) by that time or they did not have the event but had follow-up through that time point. In other words, subjects will be included in a given analysis if it can be determined whether or not the subject would have had the event by the time point.

Formulas for calculating confidence intervals for the categorical variables are given below.

1. 100(1- α) % Exact Clopper-Pearson Confidence Interval for A Single Proportion³

$$\text{Lower Confidence Limit} = \frac{x}{x + (n - x + 1)F_{1-\frac{\alpha}{2}}(2(n - x + 1), 2x)}$$

$$\text{Upper Confidence Limit} = \frac{(x + 1)F_{\frac{\alpha}{2}}(2(x + 1), 2(n - x))}{n - x + (x + 1)F_{1-\frac{\alpha}{2}}(2(x + 1), 2(n - x))}$$

where:

n = sample size

x = number of "events"

$F_{1-\frac{\alpha}{2}}(df_1, df_2)$ = the (1 - $\alpha/2$) F - statistic for degrees of freedom df_1 and df_2

2. 100(1- α) % Newcombe Score Confidence Interval for the Difference of Two Proportions⁴

a. 100(1- α) % Wilson Score Confidence Interval for A Single Proportion⁵

$$\text{Lower Confidence Limit} = \left(\hat{p} + Z_{\alpha/2}^2 / 2n - Z_{\alpha/2} \sqrt{(\hat{p}(1 - \hat{p}) + Z_{\alpha/2}^2 / 4n) / n} \right) / \left(1 + Z_{\alpha/2}^2 / n \right)$$

$$\text{Upper Confidence Limit} = \left(\hat{p} + Z_{\alpha/2}^2 / 2n + Z_{\alpha/2} \sqrt{(\hat{p}(1 - \hat{p}) + Z_{\alpha/2}^2 / 4n) / n} \right) / \left(1 + Z_{\alpha/2}^2 / n \right)$$

where:

$$\hat{p} = x / n$$

n = sample size

x = number of "events"

$Z_{\alpha/2}$ = 100(1 - $\alpha/2$)th percentile of the standard normal distribution

b. 100(1- α) % Newcombe Score Confidence Interval for the Difference of Two Proportions⁴

$$\text{Lower Confidence Limit} = (\hat{p}_1 - \hat{p}_2) - Z_{\alpha/2} \sqrt{L_1(1-L_1)/n_1 + U_2(1-U_2)/n_2}$$

$$\text{Upper Confidence Limit} = (\hat{p}_1 - \hat{p}_2) + Z_{\alpha/2} \sqrt{U_1(1-U_1)/n_1 + L_2(1-L_2)/n_2}$$

where:

\hat{p}_1 = sample proportion for group 1

\hat{p}_2 = sample proportion for group 2

L_1 and U_1 are the lower and upper Wilson Score confidence limits for p_1

L_2 and U_2 are the lower and upper Wilson Score confidence limits for p_2

$Z_{\alpha/2}$ = 100(1 - $\alpha/2$)th percentile of the standard normal distribution

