2.1.1 Statistics for Continuous Variables

For continuous variables (e.g., age, percent diameter stenosis, and lesion length), results within treatment arm will be summarized with the numbers of observations, means, and standard deviations, and in addition, with medians, quartiles, minimums, maximums, and 95% confidence intervals for the means, when specified. Differences between the treatment arms, when specified, will be summarized with the differences of the two means and 95% confidence intervals for the difference between the means, and p-values from t-test may also be presented for hypothesis generating purposes.

Formulas for calculation of the confidence intervals for the continuous variables are given below:

1. 100(1- α)% Confidence Interval For A Single Mean²

$$\bar{x} \pm t_{\frac{\alpha}{2}} \frac{s}{\sqrt{n}}$$

where:

\bar{x} = sample mean

s = sample standard deviation

n = sample size

$t_{\frac{\alpha}{2}}$ = the alpha/2 t - statistic for n – 1 degrees of freedom

2. 100(1- α)% Confidence Interval For The Difference of Two Means Under The Assumption Of Equal Variances Between The Two Groups²

$$(\bar{x}_1 - \bar{x}_2) \pm t_{\frac{\alpha}{2}} \sqrt{s_p^2 \left(\frac{1}{n_1} + \frac{1}{n_2} \right)}$$

where:

\bar{x}_1 = sample mean for group 1

\bar{x}_2 = sample mean for group 2

$$s_p^2 = \frac{(n_1 - 1)s_1^2 + (n_2 - 1)s_2^2}{n_1 + n_2 - 2}$$

s_1 = sample standard deviation for group 1

s_2 = sample standard deviation for group 2

n_1 = sample size for group 1

n_2 = sample size for group 2

$t_{\frac{\alpha}{2}}$ = the alpha/2 t - statistic for $n_1 + n_2 - 2$ degrees of freedom

3. 100(1- α) % Confidence Interval for the Difference of Two Means under the Assumption of Unequal Variances between the Two Groups²

$$(\bar{x}_1 - \bar{x}_2) \pm t_{\frac{\alpha}{2}} SED$$

With the degrees of freedom for the approximate t statistic is determined by Satterthwaite's formula² as follows:

$$df = \frac{(w_1 + w_2)^2}{\frac{w_1^2}{n_1 - 1} + \frac{w_2^2}{n_2 - 1}}$$

where:

\bar{x}_1 = sample mean for group 1

\bar{x}_2 = sample mean for group 2

s_1 = sample standard deviation for group 1

s_2 = sample standard deviation for group 2

n_1 = sample size for group 1

n_2 = sample size for group 2

$$SED = \sqrt{\frac{s_1^2}{n_1} + \frac{s_2^2}{n_2}}$$

$$w_1 = \frac{s_1^2}{n_1}$$

$$w_2 = \frac{s_2^2}{n_2}$$

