2.11 Documentation and Other Considerations

All analyses will be performed using SAS® for Windows, version 9.1 or higher.

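### Does the Clopper-Pearson upper limit printed in SAP section 2.1.2 give a wrong interval?

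*SAP*

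**What the plan says.** SAP section 2.1.2 summarises categorical variables within each arm by counts and percentages and, "where specified in the table mockups, with exact 95% Clopper-Pearson" intervals. The formulas are introduced with the sentence "Formulas for calculating confidence intervals for the categorical variables are given below".

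Formula 1 is headed as the exact Clopper-Pearson interval for a single proportion:

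- The lower limit has the F term "n - x + 1)F_{1-\frac{\alpha}{2}}(2(n - x + 1), 2x" in its denominator.
- The upper limit has "x + 1)F_{\frac{\alpha}{2}}(2(x + 1), 2(n - x" in its numerator. The term in its denominator has the same degrees of freedom but subscript 1−α/2.
- The list of symbols defines F only with subscript 1−α/2, as "the (1 - $\alpha/2$) F - statistic for degrees of freedom" df1 and df2. F with subscript α/2 is not defined.

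Two neighbouring conventions bear on the reading. In section 2.1.1 the t multiplier with subscript α/2 is "the alpha/2 t - statistic for" the stated degrees of freedom, and it is used as the usual positive multiplier. In formula 2 of section 2.1.2, Z with subscript α/2 is the 100(1−α/2)th "percentile of the standard normal distribution". Section 2.11 adds "All analyses will be performed using SAS".

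**The concern.** The exact upper limit has the form U = (x+1)F / [n−x + (x+1)F], with one and the same F in numerator and denominator. A formula with two different subscripts and identical degrees of freedom cannot be exact under any single rule for the subscript. If the subscript is a cumulative probability, the numerator is too small and the upper limit drops below the observed rate. If it is an upper-tail area, the denominator of the upper limit is too small and the lower limit goes wrong as well.

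The section offers these expressions as the formulas for the calculation. A programmer who coded them literally, or a validator who checked tables against them, could therefore produce or pass intervals that exclude the observed rate.

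**Working it through.** **Inputs.** α = 0.05, from the 95% level in SAP 2.1.2. Per-arm sizes n = 1287 (30 days, SAP 1.5.1) and n = 1235 (1 year, SAP 1.5.2.1). The documents give no ABSORB IV event counts, so x = 13, 64 and 129 of 1287 (about 1%, 5% and 10%) are assumptions for illustration. The plan states no Clopper-Pearson interval, so there is no figure of its own to reproduce.

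**Reference limits.** Lower = Beta quantile at 0.025 with parameters x and n−x+1. Upper = Beta quantile at 0.975 with parameters x+1 and n−x.

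**Worked case, x = 64, n = 1287 (observed 4.97%).** The degrees of freedom for the upper limit are 2(x+1) = 130 and 2(n−x) = 2446. The 2.5th and 97.5th percentiles of F are 0.7675 and 1.2664.

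- *Exact upper limit:* 65 × 1.2664 = 82.32; 82.32 / (1223 + 82.32) = 6.31%. The exact lower limit is 3.85%.
- *Reading A, subscript as cumulative probability:* 65 × 0.7675 = 49.89; 49.89 / (1223 + 82.32) = 3.82%. The lower limit is correct at 3.85%, so the interval is inverted.
- *Reading B, subscript as upper-tail area:* 82.32 / (1223 + 49.89) = 6.47%. The lower limit becomes 6.22%, so both limits lie above the estimate.
- *Reading C, each symbol by the rule the SAP attaches to its subscript:* F with subscript 1−α/2 is the (1−α/2) point, 1.2664. F with subscript α/2, read as the SAP reads Z with that subscript, is the 97.5th percentile, also 1.2664. Then U = 82.32 / (1223 + 82.32) = 6.31%, and both limits are exact.

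| x of 1287 | Exact and reading C | Reading A | Reading B |
|---|---|---|---|
| 13 | 0.54% to 1.72% | 0.54% to 0.59% | 1.62% to 1.74% |
| 64 | 3.85% to 6.31% | 3.85% to 3.82% | 6.22% to 6.47% |
| 129 | 8.44% to 11.80% | 8.44% to 8.20% | 11.71% to 12.23% |

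**All counts from 1 to n−1.** Under A the upper limit is below x/n for every x, and below the lower limit from x = 52 at n = 1287 and from x = 50 at n = 1235. Under B the lower limit is above x/n for every x, and the upper limit exceeds 100% from x = 1014 and x = 970 respectively. With the 97.5th percentile in both places of the upper limit, both limits equal the exact values for every x, to rounding.

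**Is the symbol the author's?** Three of the four F terms in formula 1 carry the '1−', and so does the only definition. The odd term otherwise matches its partner in the denominator, including the degrees of freedom. That fits a '1−' lost from a nested subscript in reading the PDF. It fits an author's slip equally well, and the text alone cannot separate the two.

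**The case for a change.** The best case for a change is that a written specification should be right as it stands. The same reading of the PDF preserved the '1−' in the lower limit, in the denominator of this fraction and in the definition, so a loss in one numerator alone is possible but not shown. Reading C applies two different rules inside one fraction, and F with subscript α/2 is never defined. The citation does not help either: the superscript on Clopper-Pearson is 3, which in the reference list is the SAS user's guide, while the Clopper-Pearson paper is number 2. If reading A were coded literally, coverage at n = 1287 would be 0.0% at true rates of 2%, 5% and 10%, against 96.5%, 96.0% and 95.4% for the exact interval. Correcting the symbol costs almost nothing.

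What stands is that the subscripts are inconsistent as they appear and that the citation numbering is loose. The zero coverage depends on someone coding by hand a reading whose upper limit always falls below the observed rate, and usually below the lower limit. Such output would be hard to miss in table review, and nothing in the documents points to hand coding. The method is fixed by its name, and a standard exact routine never uses the printed expression.

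**Conclusion.** No change to the plan is needed. The documents do not establish an error: the fault rests on one subscript in text read from a PDF, and the SAP's own convention for a subscript of α/2 turns the printed formula into the exact interval. If the source page does carry the symbol, it is a clerical slip to tidy in passing, by writing the 1−α/2 subscript in both places.

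The effect on results is nil, provided the tables use the named exact interval, as a standard SAS routine would. The documents imply this without stating it. The reach is small in any case: descriptive within-arm intervals, and only where the table mockups (not among the documents) call for them. The Farrington-Manning tests for 30-day TLF, 1-year TLF and angina do not use formula 1. Nor do the Newcombe intervals for differences between arms, which are built on Wilson limits. No margin, power figure, type I error rate or trial conclusion depends on it.

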2.1.3 Survival Analysis

2.1.3.1 General Survival Analysis

Survival analysis will be conducted to analyze time-to-event variables. Subjects without events will be censored at their last known event-free time point. Survival curves will be constructed using Kaplan-Meier estimates. Unadjusted log-rank test results will be displayed for comparison of survival distributions at 30 days, 180 days and 1, 2, 3, 4, 5, 6, 7 (1/8/9/10) years. Similar analyses will be performed for the 3-4/3-5/3-6/3-7 (3-8/3-9/3-10) year landmark endpoints.

Summary tables for safety and efficacy endpoints will include failure rates (Kaplan-Meier estimates), hazard ratios, confidence interval for the hazard ratio, and a p-value. For the primary analysis report, all available data will be used.

[REDACTED]

[REDACTED]

[REDACTED]

[REDACTED]

[REDACTED]

[REDACTED]

[REDACTED]

[REDACTED]

[REDACTED]

[REDACTED]

[REDACTED]

[REDACTED]

2.1.4 Hypothesis Testing

[REDACTED]

[REDACTED]

[REDACTED]

[REDACTED]

[REDACTED]

[REDACTED]

[REDACTED]

[REDACTED]

[REDACTED]

[REDACTED]

[REDACTED]

[REDACTED]

[REDACTED]

[REDACTED]

[REDACTED]

[REDACTED]

[REDACTED]

[REDACTED]

[REDACTED]

[REDACTED]

2.2 Subgroups for Analysis

All of the following subgroup analyses are intended for the final product IFU. All data collected will be summarized for ABSORB IV (N=2600) and the pooled population of ABSORB III primary analysis group and ABSORB IV (N=4600).

2.2.1 Sex

Sex-specific subgroup analyses⁹ will be performed on the ITT population. Baseline demographics, baseline subject characteristics, procedure information, morphology, quantitative coronary angiography, and hierarchical/non-hierarchical adverse event data will be summarized and compared between females and males.

[REDACTED]

2.2.2 Diabetes

Diabetic subgroup analysis will be performed on the ITT population. Baseline demographics, baseline subject characteristics, procedure information, morphology, quantitative coronary angiography, and hierarchical/non-hierarchical adverse event data will be summarized with descriptive statistics. Comparisons will be made between treatment arms within the following subgroups:

- Medication treated diabetes mellitus, defined as subjects treated with oral hypoglycemic agents or insulin,
- Non-medically treated diabetes mellitus
- Insulin-treated diabetes mellitus, defined as subjects treated with insulin,
- Non-insulin treated diabetes mellitus, defined as subjects not dependent on insulin,
- All diabetes mellitus, defined as any diabetics with or without medical treatment
- Non diabetes mellitus.

2.2.3 Other Subgroups

The following subgroups will be evaluated for the ITT population. The treatment comparisons in these analyses are not powered for hypothesis testing and are not meant for confirmatory inference. Baseline demographics, baseline subject characteristics, procedure information, morphology, quantitative coronary angiography, and hierarchical/non-hierarchical adverse event data will be summarized with descriptive statistics. Comparisons will be made between treatment arms within each of these subgroups.

Ethnicity:

- Non-white
- White

Age:

- Age \geq Median, Age $<$ Median
- Age <45 , ≥ 45 and <55 , ≥ 55 and <65 , ≥ 65 and <80 , and ≥ 80

Number of Target Lesion/Vessel Treated:

- Single target lesion/vessel treated, which includes subjects who had only one target lesion/vessel treated
- Dual target lesion/vessel treated, which includes subjects who had two target lesion/vessel treated
- Three target lesion/vessel treated, which includes subjects who had three target lesion/vessel treated.

Angina Status

- Acute coronary syndrome (unstable angina, NSTEMI, recent STEMI)

- Stable angina or silent ischemia
- Recent STEMI
- NSTEMI
- Unstable Angina
- Stable Angina
- Silent ischemia

Antiplatelet Therapy

- P2Y12 Receptor Inhibitor (Yes/No)
- Clopidogrel or Ticlopidine (Yes/No)
- Prasugrel or Ticagrelor (Yes/No)
- Clopidogrel (Yes/No)
- Ticlopidine (Yes/No)
- Prasugrel (Yes/No)Ticagrelor (Yes/No)

RVD by QCA

- $RVD \geq \text{Median}$, $RVD < \text{Median}$
- Small Vessel ($RVD \geq 2.25 \text{ mm}$, $RVD < 2.25 \text{ mm}$)

Implanted Device Diameter

- Device Diameter 2.5 mm vs. 3.0 mm vs. 3.5 mm

Population

- ABSORB III-like (Yes/No)
- ACS (Yes/No)

Implantation technique

- Compete PSP vs Incomplete PSP
 - The implantation technique used during the index procedure must satisfy all of the following criteria to be considered as complete PSP, otherwise it will be incomplete PSP
 1. Pre-dilatation performed
 2. QCA $RVD \geq 2.25 \text{ mm}$
 3. Post-dilatation performed with pressure $> 16 \text{ atm}$ and nominal scaffold diameter $<$ diameter of post-dilatation balloon \leq nominal scaffold diameter + 0.5 mm
- Each of the three individual component of complete PSP listed above (Yes/No)

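### SAP 2.2.3 orders between-arm comparisons by complete PSP, a stratum defined on the scaffold and settled after randomisation; it suits an Absorb-only description

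*SAP*

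**What the plan says.** SAP 2.2 gives the purpose: "All of the following subgroup analyses are intended for the final product IFU". It asks for the tables twice, once for ABSORB IV (2600) and once for ABSORB IV pooled with the ABSORB III primary analysis group (4600). SAP 2.2.3 adds that "The treatment comparisons in these analyses are not powered for hypothesis testing and are not meant for confirmatory inference", and then orders: "Comparisons will be made between treatment arms within each of these subgroups".

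Two of the listed families matter here.

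- **Implantation technique.** Complete PSP has three parts: pre-dilatation performed; QCA RVD of 2.25 mm or more; and post-dilatation above 16 atm with a balloon larger than the nominal scaffold diameter but not larger than "nominal scaffold diameter + 0.5 mm". The index procedure has to satisfy all three "criteria to be considered as complete PSP, otherwise it will be incomplete PSP". Each component is also a Yes/No subgroup, so the family has four splits.
- **Implanted device diameter.** The strata are "Device Diameter 2.5 mm vs. 3.0 mm vs. 3.5 mm".

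In the ABSORB IV Protocol Summary (Treatment Strategy), randomisation follows successful pre-dilatation and sizing of at least the first target lesion. Device choice and post-dilatation come later. Post-dilatation is strongly recommended for every Absorb lesion, at 16 atm or more. For XIENCE it is left to standard practice.

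**The concern.** A between-arm comparison inside a subgroup keeps the protection of randomisation only if membership is fixed before assignment, or is not influenced by it. Complete PSP and its third component meet neither condition. Their definition refers to one arm's device, and the act that decides membership happens after assignment under different instructions by arm.

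What is at stake is the label. A reader of the IFU would naturally take a complete-PSP row as the answer to how Absorb compares with XIENCE when the implant is done well. The row cannot answer that.

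**Working it through.** No stated sample size, power or alpha bears on this point, so there is no plan figure to reproduce. The check is a count, a reading of the definition both ways, and a set comparison.

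**Arm sizes.** ABSORB IV is 1:1, so 2600 / 2 = 1300 per arm. The ABSORB III primary group is 2:1, so 2000 × 2/3 ≈ 1333 Absorb and 2000 × 1/3 ≈ 667 XIENCE. Pooled: 1333 + 1300 = 2633 Absorb and 667 + 1300 = 1967 XIENCE, total 4600.

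**Literal reading of criterion 3.** A subject with only XIENCE implanted has no scaffold diameter and cannot qualify. *Complete* and component 3 *Yes* then hold essentially no XIENCE subjects. *Incomplete* holds nearly all 1300 (ABSORB IV) or 1967 (pooled), set against only those Absorb subjects who missed a criterion.

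**Reading scaffold as device.** Some XIENCE subjects can now qualify; the documents do not allow the number to be worked out. Absorb subjects enter largely by protocol recommendation and XIENCE subjects by operator judgement. To show the mechanism only, assume no device effect, half the patients at 3% risk and half at 7% (mean 5%), Absorb post-dilatation unrelated to risk, and XIENCE post-dilatation as below.

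| XIENCE post-dilated, low / high risk | XIENCE risk if post-dilated | Absorb − XIENCE | XIENCE risk if not | Absorb − XIENCE |
|---|---|---|---|---|
| 40% / 40% | 5.0% | 0 | 5.0% | 0 |
| 30% / 60% | (0.3×3 + 0.6×7)/0.9 = 5.67% | −0.67 points | (0.7×3 + 0.4×7)/1.1 = 4.45% | +0.55 points |
| 20% / 80% | (0.2×3 + 0.8×7)/1.0 = 6.2% | −1.2 points | (0.8×3 + 0.2×7)/1.0 = 3.8% | +1.2 points |

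Every rate in the table is assumed. Selection in the opposite direction would reverse the signs.

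**Pooled set.** The ABSORB III protocol (Protocol Summary, Lesion Treatment; section 7.3.4) gives Absorb post-dilatation guidance only for when it is necessary, with no minimum pressure in the visible text. ABSORB IV recommends it for all Absorb lesions. Membership therefore depends on the trial as well as the arm.

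**Components not affected.** Pre-dilatation is required in both arms: at least one target lesion before randomisation, and every target lesion before its device. QCA RVD of 2.25 mm or more applies equally to both arms and repeats the small-vessel cut already listed. So 2 of the 4 PSP splits are affected.

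**Fit with the protocol.** ABSORB IV asks for a post-dilatation balloon matched 1:1 to the vessel at 16 atm or more; criterion 3 asks for more than 16 atm and a balloon larger than the nominal scaffold. Taking the six vessel-to-scaffold rows of Table 2.0 (2.5→2.5, 2.75→3.0, 3.0→3.0, 3.25→3.5, 3.5→3.5, 3.75→3.5 mm), a 1:1 balloon at nominal size exceeds the scaffold only in the last row, 1 of 6. Expansion at high pressure could raise this; the SAP does not say whether nominal or expanded balloon diameter is meant.

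**Diameter strata.** SAP Table 1 lists Absorb in 2.5, 3.0 and 3.5 mm, so 3 of 3 sizes have a stratum. It lists XIENCE in 2.5, 2.75, 3.0, 3.25, 3.5 and 4.0 mm, so 3 of 6 do (3 of 5 where 3.25 mm is not offered). Table 2.0 puts 2.75 mm vessels into the Absorb 3.0 mm row, and 3.25 and 3.75 mm vessels into the 3.5 mm row. A XIENCE operator also has 2.75, 3.25 and 4.0 mm stents. Only 2.5 mm vessels go to the 2.5 mm scaffold.

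**The case against.** The strongest reply has five parts.

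- **The SAP already disclaims confirmatory use.** True, and this limits the severity. But a disclaimer about power and inference neither supplies a missing control nor makes differently selected groups alike.
- **A clarifying rule may exist out of sight.** SAP 2.1.2 refers to table mockups that are not shown, and much SAP text after 2.3 is redacted. A rule making PSP not applicable to XIENCE, or assigning the unlisted stent sizes, could sit there. This stands as a caveat, although the 2.2.3 list itself shows no redaction.
- **The literal reading is the least sensible one.** Perhaps. Yet SAP Table 1 separates scaffold from stent, and the neighbouring subgroup says device, so the word may well be deliberate. The looser reading does not rescue the comparison either, because arm-specific selection remains.
- **The diameter table is partly sound.** This stands. A reader might infer that every diameter row is invalid and should be dropped. The documents do not support that: the 2.5 mm row is roughly like for like, and the ABSORB IV small-vessel rule treats planned 2.5 mm stents and scaffolds alike before randomisation. No XIENCE sizing table is visible, so mismatch in the other two rows is inferred from the sizes available.
- **Other listed subgroups also follow randomisation**, such as number of lesions treated and possibly antiplatelet therapy. That is fair, but for these the visible text shows no arm-specific policy like the one for post-dilatation, and no definition tied to one arm's device.

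**Conclusion.** The point holds for complete/incomplete PSP and for component 3, on either reading of scaffold. On the literal reading the complete stratum lacks a control and the incomplete stratum holds nearly all of about 1300 (ABSORB IV) or 1967 (pooled) XIENCE subjects. On the device reading the arms differ by selection to an unknown extent. This assumes that no hidden rule restricts PSP to the Absorb arm.

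The diameter point is secondary: three XIENCE sizes have no visible stratum, and the 3.0 and 3.5 mm rows may not hold like vessels. The share of subjects affected is not given.

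A reader might go further and infer that these tables favour Absorb, or that they weaken the trial's main result. Neither is supported. The direction and size of any bias cannot be determined, and the primary and powered secondary endpoints do not use these strata. This is a cheap improvement to descriptive label tables.

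**What to change.** 1. Report complete PSP and component 3 descriptively within the Absorb arm only, labelled non-randomised. In the pooled 4600, show them separately by trial.
2. Keep pre-dilatation and QCA RVD of 2.25 mm or more as both-arm splits.
3. Use the listed QCA RVD subgroup, specified as the baseline measurement, for between-arm comparison by vessel size. For implanted diameter, either assign XIENCE 2.75, 3.25 and 4.0 mm to strata or label the table non-randomised.
4. Minor: align the 16 atm threshold with the protocol or give a reason for the difference, and state that balloon diameter means expanded diameter, as in the protocol's expansion-limit rule.

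The cost is SAP wording. No new data are needed, since baseline angiograms already go to the core laboratory (ABSORB IV Appendix III, footnote 8). The downside is that the IFU would carry no between-arm result by complete PSP.
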